- 2) History of conditions known to impact olfactory function:
 - a. Chronic rhinosinusitis
 - b. History of prior sinonasal or skull base surgery
 - c. Neurodegenerative disorders (Parkinson's disease, Huntington's disease, Amyotrophic lateral sclerosis, Lewy body dementia, frontotemporal dementia)
- 3) Currently using concomitant therapies specifically for the treatment of olfactory dysfunction
- 4) Inability to tolerate a needle injection into the neck
- 5) History of coexisting conditions that make SGB contraindicated:
 - a. Unilateral vocal cord paralysis
 - b. Severe COPD (FEV1 between 30-50% of predicted)
 - c. Recent myocardial infarction within the last year
 - d. Glaucoma
 - e. Cardiac conduction block of any degree
- 6) Currently taking blood thinners or antiplatelet agents
- 7) Allergy to local anesthetic
- 8) Inability to extend the neck for any reason (e.g., severe arthritis)

2.b Ethical Considerations

Patients will be informed in the informed consent process that they may or may not personally benefit from the study and that the data obtained from the study will be used to inform the future care patients with chronic COVID-19-induced olfactory dysfunction. There will be phone assistance available 24/7 during the study period to report any possible adverse reactions. There are no financial conflicts of interest.

2.c Subject Recruitment Plans and Consent Process

Adult patients with chronic COVID-19-induced olfactory dysfunction will be recruited from the Washington University School of Medicine/Barnes Jewish Hospital and the EPIC electronic medical record. Advertisements describing the study will be posted in the WU Department of Otolaryngology - Head & Neck Surgery clinic and on the Department of Otolaryngology – Head and Neck Surgery Twitter and Instagram pages.

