Eligible patients who present to clinic or respond to advertisements will be approached by a research team member to review the informed consent process and thoroughly discuss the research protocol, potential benefits, and risks of the study. The informed consent discussion will take place with the patient and any available family members over the phone or in person, whichever the potential participant prefers. Any subsequent questions or concerns from the potential participant and any family members will also be addressed at that time. After discussion, the patient will be asked to re-summarize the steps involved in the study to ensure understanding. If interested, written consent in

person will be obtained prior to undergoing SGB. Patients will be reminded that study participation is voluntary and will in no way affect their current or future care.

2.d Randomization Method and Blinding

No randomization or blinding will take place.

2.e Risks and Benefits

2.f Early Withdrawal of Subjects

During the informed consent process, participants will be informed that they may withdraw at any point during the study, including before, during, or after their first SGB. Participants will face no penalty or negative consequences for withdrawing from the study.

E3 Study Drug

3.a Description

3.b Treatment Regimen

The ultrasound-guided stellate ganglion blocks (SGBs) will be performed by [name], a board-certified anesthesiologist and pain management specialist who has extensive experience performing SGBs.

Patients will remain NPO for 8 hours prior to the block. If needed, they can take morning medications with a small sip of water. Using ultrasound guidance, the transverse process of C6 will be identified and confirmed. A 27-gauge needle will be used to localize the superficial skin with 1% lidocaine. Color-doppler will be used to identify vessels. Then, a 21-gauge ultrasound needle will be advanced using an in-plane technique from lateral to medial. After negative aspiration, a test dose of 2 ml of 1% lidocaine will be injected. If tolerated, 6-8 ml of 1% mepivacaine local anesthetic will be deposited beneath the prevertebral fascia and above the longus coli muscle. Total local anesthetic will be determined using a maximum total combined dose of 4.5mg/kg lidocaine and 4.5mg/kg mepivacaine.

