The presence of Horner's syndrome (ipsilateral ptosis, miosis, anhidrosis) will be recorded post-procedure. They should remain NPO for 2 hours post-block if they have a feeling of a lump in their throat.

The first SGB at the initial visit will be performed on the right side, and the second SGB at the Week 1 visit will be on the left side, given that the patient tolerated the first SGB.

F Study Procedures

F1 Screening for Eligibility

To determine potential eligibility for the study, the research team will query the medical record and our team's pre-existing databases of COVID-19-induced olfactory dysfunction patients based on the inclusion/exclusion criteria. The two study databases we will assess are the SCENT2 and GRACE studies within the department of otolaryngology - head and neck surgery. For those meeting the selection criteria, we will access name, telephone number, age, sex, and date/time of any upcoming clinic visits.

F2 Schedule of Measurements

The first two visits will be completed at the Clinical and Translational Research Unit (CTRU). The third visit will be completed virtually.

Role of the CTRU: Nursing staff will be needed for assistance in completion of the SGB. Additionally, all subjects will have vital signs monitored with serial blood pressures and pulse oximetry within the CTRU for 1 hr after completion of the block.

Visit 1

At the initial visit, demographic information, including age, sex, race, and length of time of dysosmia will be collected from each enrolled patient. Prior to undergoing the first SGB, participants will complete the UPSIT, ODOR questionnaire, Long-COVID Questionnaire I, and Smell and Taste Questionnaire I.

Visit 2

At one week, prior to undergoing a SGB on the contralateral side to their initial SGB, participants will be asked again to fill out the UPSIT and ODOR. They will also complete the Smell and Taste Questionnaire II, Long-COVID Questionnaire II, and describe any adverse events experienced after the first SGB.

Visit 3

The final visit will occur virtually, 1 month after the 2nd SGB, where participants will complete the UPSIT, ODOR, Smell and Taste Questionnaire II, Long-COVID Questionnaire II, and the Participant Satisfaction with Treatment questionnaire. Participants will also be asked to describe any adverse events experienced since the second SGB.

	Screening/Visit 1	Visit 2 (1 Week post 1st SGB)	Visit 3 (1 month post 2nd SGB)
Written informed consent	X		
Demographics	X		

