Inclusion/Exclusion Criteria	X		
UPSIT	X	X	X
ODOR Questionnaire	X	X	X
Long-COVID Questionnaire I	X		
Long-COVID Questionnaire II		X	X
Smell and Taste Questionnaire I	X		
SGB	X	X	
Smell and Taste Questionnaire II		X	X
Participant Satisfaction with Treatment Questionnaire		X	X
Adverse Events	X	X	X

F3 Safety and Adverse Events

3.a Safety and Compliance Monitoring

The specific monitoring plan for this study is based on the potential risk of participation and size and complexity of the planned investigation. Based on these considerations, this study will have a monitoring board comprised of [name], [name], [name], [name], and [name], the study biostatistician. The monitoring board will meet to review data after enrollment of 10 participants. All reports of a Serious Adverse Event (SAE) or an Unexpected Adverse Event will be investigated by the monitoring team and reported to Washington University HRPO according to the reporting requirements.

3.b Adverse Events

Adverse events will be tracked from the time of dose administration through post dose and at the follow up visit 3 for drug-related adverse events. All adverse events will be documented and assessed for relatedness to the study medication. The study team will monitor for adverse events on an ongoing basis. Once the team becomes aware of an adverse event, the AE will be reported according to institutional guidelines.

G Statistical Plan

G1 Sample Size Determination and Power

Sample size estimate for the proposed study is based both on feasibility and previous data on the use of SGB for non-COVID-19 post-viral olfactory dysfunction.

A power analysis was performed using Fisher's exact test in G-Power 3.1.2. With a positive response based on the previous study expected in 71% of participants,²² we estimate that a total sample size of 20 participants will result in a 95% confidence interval of 0.71 (+/- 0.21), resulting in a true response rate likely between 50% and 92%. A total of 20 participants are needed to allow us to detect with 80% power at the 2-sided alpha level of 0.05 a within-subjects response rate of 50% or more in the percent of subjects who experience a clinically meaningful change in CGI-I score.

G2 Analysis Plan

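### Exclusion 5b defines severe COPD as FEV1 30-50% of predicted, so read literally it does not exclude COPD with FEV1 below 30%

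*Combined protocol and SAP*

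**What the plan says.** Section E2 of the protocol lists the exclusion criteria. Item 5 opens with "History of coexisting conditions that make SGB contraindicated" and then gives five sub-items, a to e. Item 5b is "Severe COPD (FEV1 between 30-50% of predicted", and the parenthesis closes there with nothing about worse values. Item 5e, in the same list, is "Cardiac conduction block of any degree".

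Three other places affect how 5b works in practice:

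- Section F1, on screening: "To determine potential eligibility for the study, the research team will query the medical record" and the team's existing databases, judged against the listed criteria.
- The schedule in section F2 has a row "Inclusion/Exclusion Criteria" marked at Screening/Visit 1. It has no row for spirometry.
- Section E3, 3.b, says that the blocks are done by "a board-certified anesthesiologist and pain management specialist who has extensive experience performing SGBs".

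**The concern.** A contraindication that applies at one level of lung impairment should also apply at a worse level of the same disease. As written, 5b does the reverse below 30%: the less impaired patient is kept out and the more impaired one is not. The documents give no reason for a 30% floor, so this looks like a severity-grade label copied in with both of its limits rather than a deliberate choice.

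What is at stake is participant safety and a clear eligibility record, not the trial's inference. Each participant is due to receive two neck injections of local anesthetic. If a candidate with FEV1 below 30% came forward and was turned away, no written criterion would support that decision. If the text were applied mechanically, for example as a record query coded 30 to 50, the candidate would not be flagged.

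**Working it through.** The plan states no figure on this point, so there is nothing to reproduce. The check is a reading of the criteria, followed by a rough sizing.

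**Step 1: item 5b applied to COPD patients at three levels of FEV1 (% of predicted).**

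| FEV1 | Inside the 30-50% band? | Excluded by 5b as written? |
|---|---|---|
| Above 50% | No | No, as expected of a severity threshold |
| 30-50% | Yes | Yes |
| Below 30% | No | No |

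**Step 2: does anything else exclude FEV1 below 30%?**

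- Inclusion criteria 1-4 cover age, COVID history with self-reported smell loss, the UPSIT score, and English. None concerns lung function.
- Exclusions 1-3 cover smell loss before COVID-19, conditions that affect olfaction, and concurrent treatment for smell loss.
- Exclusion 4 is "Inability to tolerate a needle injection into the neck".
- The rest of list 5 covers vocal cord paralysis, recent myocardial infarction, glaucoma and conduction block.
- Exclusions 6-8 cover blood thinners or antiplatelet agents, anesthetic allergy, and "Inability to extend the neck for any reason (e.g., severe arthritis".
- There is no clause on very severe COPD, oxygen use, respiratory failure or investigator judgement. The opening line of item 5 ends in a colon and introduces a closed list, so it is not a separate catch-all.

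Nothing closes the gap.

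**Step 3: is the floor just the drafting style of the list?** No. Item 5e is written to take in every grade of its condition. Item 5c has a single limit (infarction within the last year). Item 5b is the only one in list 5 with a two-sided numeric band.

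**Step 4: size.** The planned sample is n = 20 (section G1). Let p be the share of otherwise eligible candidates who have COPD with FEV1 below 30%. The documents do not give p, so the values below are assumed. The expected number is 20p, and the chance of at least one is 1 - (1 - p)^20.

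| p (assumed) | Expected, 20p | 1 - (1 - p)^20 |
|---|---|---|
| 0.01% | 0.002 | 0.0020 (0.2%) |
| 0.05% | 0.01 | 0.0100 (1.0%) |
| 0.1% | 0.02 | 0.0198 (2.0%) |
| 0.5% | 0.1 | 0.0954 (9.5%) |

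These are chances that such a person would be among 20 candidates who meet every other criterion. They are not chances of enrolment or harm, which would be lower.

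**The case against.** The best case for leaving 5b alone has four parts.

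*The wording is less open than it looks.* Item 5 asks about a history of the listed conditions. Someone now below 30% whose record shows an earlier value of 30-50% is arguably excluded on the text as it stands. This is fair and narrows the gap, but a patient first measured below 30% is still not covered.

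*The intent is obvious.* The operative words are severe COPD under a contraindication heading, and a clinician would have to treat worse disease as not severe in order to enrol the patient. This stands, and it makes the point one of wording rather than design. It supports correcting the text, because screening is done against the written criteria.

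*Other safeguards exist.* Eligibility is checked at Visit 1 and an experienced specialist does the block. A test dose comes before the full dose. The two sides are done a week apart, the second only if the first was tolerated, and blood pressure and pulse oximetry are followed for 1 hour after each block. These make wrong enrolment unlikely or limit its consequences. However, the Visit 1 check uses the same text, and the procedural safeguards act only after a patient has been admitted.

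*The numbers are soft.* Nothing in the documents anchors either end of the range for p, and the 9.5% comes entirely from the assumed upper end. This is correct, and the point does not depend on the range.

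The lack of spirometry would also apply to the corrected wording. It means only that 5b is applied to whatever FEV1 is already on record.

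**Conclusion.** The point holds as a minor wording error in a safety criterion. Read literally, COPD with FEV1 below 30% of predicted is not excluded by 5b or by any other criterion, at least for a patient with no earlier value in the 30-50% band. That conclusion rests on the text alone.

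The likely effect in a study of 20 is very small: at most about 0.1 expected candidates under the assumed range, and fewer once the Visit 1 check and the operator's judgement are allowed for. It has no bearing on the sample size, the primary outcome or the analysis. It is worth correcting because the criterion exists to protect participants and the correction costs almost nothing.

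**What to change.** Remove the lower limit and keep the protocol's own upper limit. Item 5b could read: *Severe or very severe COPD (FEV1 at or below 50% of predicted)*. Any screening query or eligibility checklist built from the 30-50% band should be changed to match, and later studies that reuse these criteria should carry the corrected wording.

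The cost is a one-line change to the eligibility text. Visits, procedures, sample size and analysis stay as they are.

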Clinical Global Impression - Improvement Scale (CGI-I). The overall response to treatment will be measured with the *CGI-I* scale. The *CGI-I* Scale measures response to treatment for a number of disorders and has good internal consistency and validity. {Dunlop, 2017, Transdiagnostic Clinical Global Impression Scoring for Routine Clinical Settings} The *CGI-I* scale measures change in clinical condition based on a 7-point Likert scale and will be modified as seen in the Appendix. The primary outcome measure of the study will be the proportion of participants within each *CGI-I* for smell loss group at 1 month. Responders will be identified as those reporting moderate improvement or greater.

Long-COVID Questionnaire. We will assess the following 11 symptoms of Long COVID other than olfactory and gustatory dysfunction: tiredness/fatigue, shortness of breath, brain fogginess, headache, cough, depression, low-grade fevers, palpitations, dizziness,

muscle pain, and joint pains. All 11 symptoms will be asked to rank the level of severity with answer choices from *No problem* to *Severe problem*. The Long-COVID questionnaire will be administered at all 3 visits. See Appendix for questionnaires.

Patient Satisfaction with Treatment. Patients will be asked at the final visit, “Overall, how satisfied were you with the stellate ganglion block treatment for your smell loss?” Possible answer choices: 1) Completely dissatisfied, 2) Mostly dissatisfied, 3) Somewhat dissatisfied, 4) Neither satisfied or dissatisfied, 5) Somewhat satisfied, 6) Mostly satisfied, 7) Completely satisfied. Patients will also be asked at the final visit, “Would you recommend this treatment to a family member or close friend who also suffers from chronic smell loss due to COVID-19?” Possible answer choices: 1) Yes, 2) No.

Adverse Events. Participants will be asked to describe any adverse events experienced after both SGB procedures. Additionally, any adverse events noted at the time of SBG will be noted.

D Investigational Agent

D1 Clinical Data to Date

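### Does dating Visit 3 only from the second block leave one-block participants without a primary assessment?

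*Combined protocol and SAP*

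**What the plan says.** Section C3 makes the primary outcome the distribution of CGI-I "for smell loss group at 1 month. Responders will be identified as those reporting moderate improvement or greater". It does not say what the month is counted from. CGI-I is part of the Smell and Taste Questionnaire, which C3 assigns to all three visits; version II is the post-baseline form, used at Visits 2 and 3.

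Section F2 dates the last visit: "The final visit will occur virtually, 1 month after the 2nd SGB". The schedule table repeats this in its column header, "Visit 3 (1 month post 2nd SGB". Section E3, 3.b makes the second block conditional: "the second SGB at the Week 1 visit will be on the left side, given that the patient tolerated the first SGB".

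At Week 1, before that second block, "participants will be asked again to fill out the UPSIT and ODOR. They will also complete the Smell and Taste Questionnaire II". The Visit 3 safety question is framed the same way as the visit: "Participants will also be asked to describe any adverse events experienced since the second SGB". Section F3, 3.b is more general: "Adverse events will be tracked from the time of dose administration through post dose and at the follow up visit 3".

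Section 2.f covers leaving the study, telling participants that "they may withdraw at any point during the study, including before, during, or after their first SGB". It does not mention missing the second block while staying in follow-up. Section G2 applies intention to treat and measures improvement relative to the time before a block, in the singular.

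**The concern.** Read literally, these sections leave a hole. The 1-month CGI-I comes only from Visit 3, Visit 3 is counted only from the second block, and the second block depends on tolerating the first. The protocol therefore foresees a participant with one block but gives that person no date for the primary rating. The Week 1 questionnaire is not a substitute, because it is not the primary time point.

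The only efficacy figure is a single-arm proportion in 20 people, so each person is worth 1/20 = 5 points. If one-block participants were left out and responded less often than the rest, the proportion would be too high; if they responded more often, too low. The loss could be informative, because it would be linked to how the first block was tolerated. A rating that was never taken also cannot be recovered at analysis. The safety question has a similar flaw: a one-block participant has no second block to count from.

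**Working it through.** **Is Visit 3 meant for everyone dosed?** Five places bear on this:

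- C3 gives the smell and taste questionnaires at all three visits, without exception.
- F2 introduces the third visit as a virtual one, with no condition attached.
- F3, 3.b follows adverse events to Visit 3 for everyone dosed.
- C3 sets the primary time point at 1 month without tying it to the second block.
- G2 uses intention to treat and does not require two blocks.

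Together they describe a visit that everyone dosed is to have. Nothing tells staff to skip it. Only the date is unstated when there was no second block.

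**The plan's own precision (G1).** Inputs: N = 20, expected response 71%, stated interval 0.71 ± 0.21.

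Half-width = t(0.975; 19 df) × √(0.71 × 0.29 / 20) = 2.093 × 0.1015 = 0.212, giving 0.498 to 0.922. This matches the stated 50% to 92%.

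**Shift if k one-block participants are left out.** Let the others respond at 71% and the omitted k at rate q, which is an assumption.

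Shift = 0.71 − [0.71 × (20 − k) + q × k] / 20 = k × (0.71 − q) / 20

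| k | q = 0 | q = 35.5% | q = 71% |
|---|---|---|---|
| 1 | +3.55 points | +1.78 | 0 |
| 2 | +7.10 points | +3.55 | 0 |

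A whole-number example for k = 1, with the omitted person a non-responder: 14/19 = 73.7% (exact 95% CI 48.8% to 90.9%) against 14/20 = 70.0% (45.7% to 88.1%).

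**How many might be affected?** The documents give no rate for missing the second block. As rough proxies I take the complication counts in sections B and D2: 0 of 38, 1 of 37, and 0 of 250 procedures. Pooled, this is 1/325; the first two alone give 1/75; the least favourable series gives 1/37. Then P(none of 20) = (1 − p)^20, expected k = 20p, and the expected worst-case shift = 20p × 3.55 points.

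| p | P(none) | Expected k | Expected worst-case shift |
|---|---|---|---|
| 1/325 | 94% | 0.06 | 0.2 points |
| 1/75 | 76% | 0.27 | 0.9 points |
| 1/37 | 58% | 0.54 | 1.9 points |

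The chance of two or more is 0.2%, 2.9% and 10.1%.

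**A harsher assumption.** D2 reports that 95% of 110 survey respondents would accept as many repeat procedures as needed. If the other 5% are all treated as missing the second block, expected k = 20 × 0.05 = 1, P(none) = 0.95^20 = 36%, and the expected worst-case shift is 3.55 points. That is still about one sixth of the planned half-width (3.55/21 = 0.17).

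**The case for a change.** The strongest reply is that a protocol should not rely on staff to guess a visit date, above all for the primary outcome, and that the remedy would cost only a few words because Visit 3 is already virtual. Intention to treat argues against a completers-only result, but it neither schedules a rating nor says how a missing one counts. The proxies are also weak. They count complications, whereas intolerance could be wider; the 250 are procedures rather than people; and nothing says that the one temporary complication prevented a further block.

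It stands that no date is written and that the frequency is uncertain. That does not amount to a fault in the design. Dating the visit from the second block suits an aim stated in terms of sequential blocks. A participant with one block can still be reached a month later and can still answer, because CGI-I asks about change from before treatment; the rating would come about one week sooner after baseline than for the others. The safety wording is editorial: Visit 2 asks about events after the first block, F3 has the team monitoring continuously, and section 2.b provides a telephone line at all hours.

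A rule for missing outcomes is a different matter. It chiefly concerns people who withdraw, whom no re-dating of Visit 3 would recover. Counting a missing rating as non-response is only one defensible choice: at 71% response it lowers the estimate by an expected 0.71/20 = 3.55 points per person, as much as the worst-case bias it would guard against for one participant.

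**Conclusion.** The concern does not call for a change. The protocol omits a Visit 3 date for a participant who has one block and stays in follow-up, but its other sections show that this person is expected at Visit 3 and belongs in the analysis. This is a missing detail that the study team can fill sensibly, not a scheduled loss of the primary outcome.

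Even if one such person were left out, the proportion would move by at most 3.6 points, and by nothing if that person's chance of response matched the others'; the planned precision is ±21. The expected worst-case shift is about 0.2 to 1.9 points on the complication proxies and 3.6 points on the harsher 5% assumption. These figures rest on 71% response among the others, on every omitted participant being a non-responder, and on proxies that do not measure the affected group directly. The conclusion would weaken only if several of the 20 missed the second block, stayed in the study and were then never called, and nothing in the documents points to that. This takes no view on who should receive the second block.

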Most recently, anecdotal news reports and a published case series point to a possible beneficial effect of SGB on both chronic COVID-19-induced olfactory dysfunction and various other long COVID symptoms. A published case series by Liu et al describes two patients who underwent SGB for long COVID symptoms, including olfactory dysfunction.²⁴ SGB was performed on the right side then either one or two days later to the left side. Both patients reported significant and durable improvement in symptoms, including fatigue, “brain fog,” and olfactory and gustatory dysfunction that persisted at 60-day follow-up. Nearly all other long COVID symptoms, including cough, chest pain, heart palpitations, and orthostatic dizziness, also improved at the one week and two-month follow-up time points. The authors concluded that although the sample size is limited, SGB may have a significant impact on the dysautonomia caused by COVID-19 and improve long COVID symptoms, giving rationale to conduct a larger study. Therefore, we propose a single cohort prospective study to generate pilot data on the effectiveness and safety of sequential stellate ganglion blocks for the treatment of COVID-19-induced olfactory dysfunction and other long COVID symptoms.

C Study Objectives

C1 Primary Aim

1. The effectiveness of a sequential SGB in improving both self-reported and objective olfactory dysfunction

C2 Secondary Aim

2. The effectiveness of a sequential SGB in improving other self-reported long COVID symptoms, including fatigue, dyspnea, cough, impaired memory and

concentration, muscle pain, headache, heart palpitations, depression/anxiety, fever, orthostatic dizziness, and post-exertional malaise

3. The safety and tolerability of a sequential SGB

C3 Rationale for the Selection of Outcome Measures

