heart palpitations, and orthostatic dizziness, also improved at the one week and two-month follow-up time points. The authors concluded that although the sample size is limited, SGB may have a significant impact on the dysautonomia caused by COVID-19 and improve long COVID symptoms, giving rationale to conduct a larger study. Therefore, we propose a single cohort prospective study to generate pilot data on the effectiveness and safety of sequential stellate ganglion blocks for the treatment of COVID-19-induced olfactory dysfunction and other long COVID symptoms.

D2 Dose Rationale and Risk/Benefits

The stellate ganglion block has been used for decades with the assistance of fluoroscopy and has been modified in the present day by using ultrasound to improve visualization. Substantial data has been generated on the safety and tolerability of the procedure in other conditions, such as post-traumatic stress disorder (PTSD). One study of 250 SGBs for PTSD performed by an experienced pain management provider resulted in zero post-procedural or delayed complications. Of 110 participants in the study who returned completed surveys, 100% of the patients said they would recommend the procedure to a friend, and 95% stated that they would be willing to undergo as many repeat procedures as necessary based on the minimal discomfort and tolerable side effects.²⁸ A temporary Horner's syndrome is an expected outcome of SGB and improves over the course of a few hours.

Risks of lidocaine injection include: drowsiness, dizziness, nausea, vomiting, feeling hot or cold, confusion, ringing in your ears, blurred vision, or double vision. However, these side effects are all rare when used at the maximum total combined dose of 4.5mg/kg lidocaine and 4.5mg/kg mepivacaine. We will strictly following this dosing guideline.

E Study Design

E1 Overview or Design Summary

The study will be a single center, unblinded, prospective cohort study conducted at Washington University School of Medicine.

E2 Subject Selection

2.a Inclusion Criteria

- 1) Adults age 18 to 70
- 2) Diagnosis of COVID at least 12 months prior to study enrollment with self-reported olfactory dysfunction
- 3) Objective olfactory dysfunction due to COVID-19 that has persisted despite viral recovery, as defined by the UPSIT (≤ 34 in women, ≤ 33 in men)

-
- 4) Ability to read, write, and understand English

2.a Exclusion Criteria

- 1) History of smell loss prior to COVID-19 infection

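### Scheduled enquiry about post-discharge adverse events comes 1 week after the first block but only 1 month after the second, so mild transient events after the second block may be under-reported.

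*Combined protocol and SAP*

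**What the plan says.** C2 lists as a secondary aim "The safety and tolerability of a sequential SGB", and the primary hypothesis in A2 includes safety.

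F2 sets the scheduled enquiries. At Visit 2, one week after the first block and before the second, participants attend the CTRU and "describe any adverse events experienced after the first SGB". For the second block: "The final visit will occur virtually, 1 month after the 2nd SGB", and at that visit "Participants will also be asked to describe any adverse events experienced since the second SGB". The schedule table marks adverse events at Visits 1, 2 and 3 and shows no contact between Visits 2 and 3.

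Other provisions apply to each block:
- C3, Adverse Events: "any adverse events noted at the time of SBG will be noted".
- F2, role of the CTRU: "serial blood pressures and pulse oximetry within the CTRU for 1 hr after completion of the block".
- E3, 3.b Treatment Regimen: "The presence of Horner's syndrome (ipsilateral ptosis, miosis, anhidrosis) will be recorded post-procedure".
- E2, 2.b Ethical Considerations: a phone line open at all hours for reporting possible reactions.
- F3, 3.b: tracking from dosing through an undefined post-dose period and at Visit 3, plus ongoing monitoring with no contact or interval named.

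**The concern.** The effects the plan itself mentions are mostly brief. D2 says: "A temporary Horner's syndrome is an expected outcome of SGB and improves over the course of a few hours". D2 also lists short-term effects of lidocaine, E3 mentions a lump-in-the-throat feeling after the block, and the background cites a temporary brachial plexus block in an earlier study. A participant asked a month later may not mention a mild effect that lasted hours or a day, whereas the same effect after the first block is asked about within a week.

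The second block is what makes the treatment sequential, and it has the longer recall interval. In a pilot of 20, one or two unreported events could alter the tolerability statement, and what was not asked in time cannot be recovered later.

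Any tabulation by block would also mix the block with the enquiry interval. E3 fixes the right side first and the left side second, and gives the second block only to those who tolerated the first.

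**Working it through.** The plan states no figure on this point, so there is none to reproduce. The check sets the collection points for the two blocks side by side.

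| Source | After block 1 | After block 2 |
|---|---|---|
| Events noted at the procedure (C3) | yes | yes |
| Horner's presence recorded (E3, 3.b) | yes | yes |
| Monitoring in the CTRU (F2) | 1 hour | 1 hour |
| Phone line, participant-initiated (E2, 2.b) | yes | yes |
| Scheduled question (F2) | 1 week, in person | 1 month, virtual |

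Only the last row differs. Taking a month as 30 days, the ratio of intervals is 30/7 = 4.3. The events exposed to the difference are those that start or persist after the monitored hour, are mild enough not to prompt a call, and resolve well before Visit 3.

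The documents give no rate for such events and no recall rate. What follows is illustration only. Inputs: n = 20 (G1), assuming all 20 receive the second block; r, the true proportion with such an event after that block (assumed); s, the share of those events reported at 1 month (assumed).

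- Expected reports = n × r × s.
- Chance of at least one report = 1 − (1 − r × s)^20.
- With no reports in 20, the one-sided 95% upper limit for the reported proportion is 1 − 0.05^(1/20) = 13.9%. Since the reported proportion is r × s, the limit for the true proportion is 13.9%/s.

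| s | Expected, r = 10% | Chance of ≥1, r = 10% | Expected, r = 20% | Chance of ≥1, r = 20% | Upper limit if 0 of 20 |
|---|---|---|---|---|---|
| 1 | 2.0 | 0.88 | 4.0 | 0.99 | 13.9% |
| 0.9 | 1.8 | 0.85 | 3.6 | 0.98 | 15.5% |
| 0.75 | 1.5 | 0.79 | 3.0 | 0.96 | 18.5% |
| 0.5 | 1.0 | 0.64 | 2.0 | 0.88 | 27.8% |

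For example, at r = 10% and s = 0.5: 20 × 0.10 × 0.5 = 1.0 expected report, and 1 − 0.95^20 = 0.64. At r = 5% the chance of at least one report runs from 0.64 (s = 1) to 0.40 (s = 0.5).

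**The case against.** The strongest reply is that most of what matters is caught on site, equally for both blocks. Horner's syndrome, the most obvious short-lived effect, is recorded by staff, so its presence does not depend on memory. Lidocaine effects or a lump in the throat that appear during the procedure or the monitored hour would be noted. The phone line is always open. This stands, and it confines the point to mild post-discharge events. It does not remove the point: the phone line relies on the participant to call, and the ongoing monitoring in F3 names no contact.

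A reader might infer that events after the second block are known only from recall at 1 month. The sources listed above contradict that.

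A reader might also infer that events are certain to be under-counted, or that the second block will look better tolerated. The documents support neither. They give no recall rate, and the 30-day window can also collect late or unrelated events that a 7-day window misses, so the net direction is open.

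Finally, no comparison of one block with the other is planned. Aim 3 concerns the sequence as a whole, and G2 specifies no such contrast. That stands too: the main consequence is possible under-reporting in the overall safety description, and the unequal windows matter only if events are tabulated by block.

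**Conclusion.** The point holds in limited form. Scheduled enquiry is about 7 days after the first block and about 30 days after the second, with nothing described in between. Mild, transient events after the second block that start or persist after discharge and are not phoned in may be under-reported, and event counts by block would rest on unequal windows.

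The size of any shortfall cannot be derived. The illustration suggests a loss of one report or fewer if 10% have such an event and at least half are reported, and of up to two reports if 20% do. Those rates are assumptions, and the calculation treats all 20 participants as receiving both blocks.

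This is an optional-to-moderate improvement to a descriptive secondary aim in a single-arm pilot. It does not touch the primary endpoint.

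**What to change.** In F2 and the schedule table, add one remote adverse-event enquiry, by electronic survey or short call, about 1 week after the second block. Use exactly the Visit 2 question, changing only which block it refers to. If named effects are prompted, prompt them at both 1-week enquiries; prompting at one alone would create a new imbalance.

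In G2, state that adverse events will be reported for each block over the common 1-week window and by source (observed on site, solicited, spontaneous), with later events from Visit 3 listed separately.

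The cost is 20 short contacts, which the existing REDCap database could support, and possibly a slightly higher adverse-event count. No visit or procedure is added, and sample size and power are unchanged. The mode would still differ (in person versus remote) unless the Visit 2 question is put on the same form.
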